9.3 Study timetable and end of study

Projected study timelines are as the following:

Research Agreement executed: Oct 30, 2016

Projected IRB/IEC approval: Nov 30, 2016

First Subject In: Dec 30, 2016

50% Enrollment: Sep 30, 2017

Last Subject In (100% enrollment): Jun 30, 2018

Last Subject Last Visit (Treatment end): Dec 30, 2018

Publication: Mar 30, 2019

10. DATA MANAGEMENT

Case Report Forms / Electronic Data Record

As used in this protocol, the term case report form (CRF) should be understood to refer to either a paper form or an electronic data record or both, depending on the data collection method used in this trial.

A CRF is required and should be completed for each included subject. It is the investigator's responsibility to ensure completion and to review and approve all CRFs. CRFs must be signed by the investigator or by an authorized staff member. These signatures serve

to attest that the information contained on the CRFs is true. At all times, the investigator has final personal responsibility for the accuracy and authenticity of all clinical and laboratory data entered on the CRFs. Subject source documents are the physician's subject records maintained at the trial site. In most cases, the source documents will be the hospital's or the physician's chart. In cases where the source documents are the hospital or the physician's chart, the information collected on the CRFs must match those charts.

In some cases, the CRF may also serve as the source document. In these cases, the investigator must prospectively document which items will be recorded in the source documents and for which items the CRF will stand as the source document.

11. EVALUATION AND CALCULATION OF VARIABLES

NA

11.1 Calculation or derivation of efficacy variable(s)

NA

11.2 Calculation or derivation of safety variable(s)

NA

11.2.1 Other significant adverse events (OAE)

NA

11.3 Calculation or derivation of patient reported outcome variables

NA

11.4 Calculation or derivation of pharmacokinetic variables

NA

11.5 Calculation or derivation of pharmacodynamic variable(s)

NA

11.5.1 Calculation or derivation of the relationship between pharmacokinetic and pharmacodynamic variables

NA

11.5.2 Population analysis of pharmacokinetic/pharmacodynamic variables

NA

11.6 Calculation or derivation of pharmacogenetic variables

NA

11.7 Calculation or derivation of health economic variables

NA

12. STATISTICAL METHODS AND SAMPLE SIZE DETERMINATION

12.1 Description of analysis sets

12.1.1 Efficacy analysis set

The primary efficacy analysis set will be based on a pharmacodynamic set such that subjects must have non-missing observations of study endpoints in both periods. A secondary analysis will be performed on the intent-to-treat (ITT) set which includes all patients who receive at least 1 dose of treatment.

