The data management plan for this project is based on the randomization of 45 participants, with randomization occurring at the time of Visit 2. All candidates who complete the informed consent process will be assigned a study identification number (ID) at the time of Visit 1. Unless otherwise stipulated by the sponsor-investigator, the ID numbers are patient-specific and will be retained and associated with candidates who fail screening or are found to be ineligible, and/or drop-out prior to randomization. Follow-up will not be continued for candidates who do not proceed to randomization. Follow-up and research activities will be pursued on all randomized participants, even those candidates who may for some reason stop research medications.

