5.8.1 Procedures for discontinuation of a subject from investigational product

If the study patient withdraws consent or who fails to comply with the study protocol or becomes pregnant, participation in the study will end and the study medication will be stopped. No further evaluation will be performed and no attempts should be made to collect additional data.

If a patient develops UTI or genital infection, we will manage the infection according to standard of care. However, a patient with persistent or recurrent UTI or genital infection despite standard of care, study medications will be hold temporarily until infections resolve. If a patient develops persistent serious adverse effects from study drugs (section 6.4.2 and 6.4.4), study medications will be discontinued permanently. And patients will be followed up until their serious adverse effects are completely resolved.

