5.9 Withdrawal from study

A subject may withdraw from the trial at any time at their own request, or they may be withdrawn at any time at the discretion of the investigator for safety, behavioral, or

administrative reasons. If a subject does not return for a scheduled visit, every effort should be made to contact the subject. In any circumstance, every effort should be made to document subject outcome, if possible.

If the subject withdraws consent, no further evaluations should be performed and no attempts should be made to collect additional data; however, they may be questioned regarding their reason for withdrawal and asked to return all unused investigational products.

Patients who withdraw or discontinue from the trial after randomization will not be replaced.

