12.2 Methods of statistical analyses

The primary objective of this trial is to compare the change in the LF: HF ratio from baseline to 12 weeks for patients on dapagliflozin versus glimepiride.

The mean change in LF: HF ratio for each drug from baseline to 12 weeks will be reported with the corresponding 95% confidence interval. The mean difference between drugs of changes from baseline to 12 weeks and the corresponding 95% confidence interval will also be reported. The change from baseline to 12 weeks within each period (between drugs) will be compared within patients using a two-sided t-test (applying transformations where appropriate; using the pharmacodynamics set of subjects). This analysis will be repeated using the ITT set of subjects. If there is chance within-subject or between-subject imbalance in baseline measures (such as glucose control, BMI and age), we will use the ANCOVA method including those unbalanced covariates to improve precision (Metcalf, *Statistics in Medicine, The analysis of cross-over trials with baseline measurements*, 2010).

A corresponding primary analysis to the t-test controlling for possible sequence and period effects includes a linear mixed effects model (also known as random effects model; applying transformations where appropriate) with outcome of the change in LF: HF ratio from baseline to 12 weeks. This model assesses the difference between drugs by accounting for a

random effect for subject (nested within sequence) and fixed effects for treatment, sequence, and period.

We will additionally explore differences between the drugs over time using all of the data measured at baseline, 4, 8 and 12 weeks with a linear mixed model. The outcome will be the change from baseline at 4, 8 and 12 weeks. The model will include a random term for subject nested within sequence and fixed effects for treatment, sequence, visit, period, and interaction terms for visit by treatment. The interaction terms for visit by treatment provide estimates of treatment effects at each visit. An unstructured variance/covariance matrix will be used.

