12.3 Determination of sample size

We assume there are no carryover effect and no interactions between patients, treatments, and time period. For each patient in each period (on each drug), the LF: HF ratio will be measured at baseline and at 12 weeks. The primary outcome will be the difference between periods (drugs) in the differences from baseline to 12 weeks of the LF: HF ratio (i.e. [LF: HF sulfonylurea, week12 – LF: HF sulfonylurea, baseline] – [LF: HF dapagliflozin,

week12 – LF: HF dapagliflozin, baseline]). Based on previous studies, we have found the LF: HF ratio to have a mean of 3.4 (SD=2.1) for those with T2D. Assuming a similar within person standard deviation (2.1) of the difference of the differences in the LF: HF ratio from baseline to 12 weeks, we have 80% power with 38 patients to find a difference between the two drugs in the differences in LF: HF ratios of 1.4 using a two-sided (paired) t-test at the 0.05 significance level (sample size from applet available at http://hedwig.mgh.harvard.edu/sample_size/js/js_crossover_quant.html). Expecting 10% of the subjects to not complete the entire study, we plan to enroll 45 patients.

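### The ITT repeat of the paired t-test cannot use one-period patients, the 12-week mixed model that could has no named analysis set, and Section 5.8.1 conflicts with 5.3 and 5.9 on data collection after non-compliance

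*Combined protocol and SAP*

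**What the plan says.** **Analysis sets (12.1.1).** The primary efficacy set requires that "subjects must have non-missing observations of study endpoints in both periods". The secondary ITT set is everyone who took at least one dose.

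**Analyses (12.2).** The change in LF:HF from baseline to week 12 is compared between drugs by a two-sided within-patient t-test on the both-period set. Then: "This analysis will be repeated using the ITT set of subjects". No imputation or other missing-data rule is given. The next paragraph adds: "A corresponding primary analysis to the t-test controlling for possible sequence and period effects includes a linear mixed effects model". That model has a random subject effect and fixed treatment, sequence and period effects; no analysis set is named for it. A further longitudinal mixed model, described as exploratory, is to use all data at baseline and weeks 4, 8 and 12.

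**Expected losses.** Section 12.3: "Expecting 10% of the subjects to not complete the entire study, we plan to enroll 45 patients". Section 5.9: "Patients who withdraw or discontinue from the trial after randomization will not be replaced".

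**Data collection after stopping.** Three sections give rules:
- Section 5.3: "Follow-up and research activities will be pursued on all randomized participants, even those candidates who may for some reason stop research medications".
- Section 5.8.1, for withdrawn consent, failure to comply with the protocol, or pregnancy, ends participation and adds: "No further evaluation will be performed and no attempts should be made to collect additional data".
- Section 5.9 applies the ban to one case only: "If the subject withdraws consent, no further evaluations should be performed and no attempts should be made to collect additional data".

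**The concern.** A second analysis labelled ITT, set beside a completers' analysis, will be read as showing whether the result survives drop-out. Here it cannot show that. The primary set selects on something that happens after randomization, namely providing data in both periods. The planned check applies a method that makes the same selection again.

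The second half of the problem comes earlier, at data collection. If a non-compliant patient who still consents is handled under 5.8.1, the remaining LF:HF measurements are never taken, and no later analysis can restore them. If the same patient is handled under 5.3, they are taken. Staff have both instructions.

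What is at stake is mainly selection in the primary comparison and false reassurance from a duplicate result. Precision is a minor matter.

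**Working it through.** **1. The plan's own figure.** Inputs from 12.3: difference 1.4, SD 2.1, two-sided 0.05, 80% power, 38 patients, 10% loss, 45 enrolled. With 2.1 as the SD of one period's change within a patient, the paired difference has SD 2.1 × √2 = 2.97. The noncentral t then gives 80.8% power at n = 38, so the stated 38 reproduces. With 2.1 as the SD of the paired difference itself, 20 patients would be enough. I therefore use 2.97 below.

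**2. Who enters the ITT t-test.** The t-test needs d = (glimepiride change) − (dapagliflozin change) for each patient. With one period missing and no imputation, d does not exist.
- If the both-period rule is read per endpoint, patients with a usable d are the same in both sets. In a simulated set of 45 with 5 missing period 2, the t-test on all 45 and on the 40 complete patients gave the same t (−2.086), df (39) and p (0.044).
- If the rule means every study endpoint, a patient with both LF:HF changes but, say, a missing BNP could re-enter. One-period patients still could not.
- Mean changes per drug could differ between the sets, if the repeat covers them.

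**3. How many are affected.** 45 × 0.10 = 4.5, so 4 or 5 patients, from all causes.

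**4. Precision if the 12-week mixed model used them.** Take 40 complete patients and 5 with period 1 only, split 2/3 by sequence. Let rho be the correlation between a patient's two period changes. The documents do not give it, so I take 0 to 0.8.

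| Analysis | SE | Equivalent pairs | Power |
|---|---|---|---|
| Paired t-test, either set | 0.470 | 40 | 82.8% |
| Mixed model, rho 0 | 0.456 | 42.3 | 84.8% |
| Mixed model, rho 0.5 | 0.463 | 41.1 | 83.8% |
| Mixed model, rho 0.8 | 0.467 | 40.5 | 83.2% |

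The gain is about 0.5 to 2.3 pairs, or 0.4 to 2 points of power.

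**5. Illustrative selection shift.** Suppose drop-outs' drug difference is 1.4 away from completers'. This is an assumption. Completer shift = (m/45) × 1.4:
- m = 4: 0.124, or 8.9% of 1.4. SE at n = 41 is 2.97/√41 = 0.464; ratio 0.27.
- m = 5: 0.156, or 11.1% of 1.4. SE at n = 40 is 2.97/√40 = 0.470; ratio 0.33.

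**6. How much the mixed model recovers.** With period 2 lost, each sequence's period-1 minus period-2 contrast equals the completers' contrast plus (1 − rho) × (period-1 mean of all − period-1 mean of completers). Half the difference between sequences gives the completer estimate plus (1 − rho)/2 × shift, if losses are balanced over sequences. Recovery is thus 50% at rho 0 and 25% at rho 0.5: 0.062 and 0.031 for m = 4, 0.078 and 0.039 for m = 5. At rho 0.8 it is 10%.

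Recovery is complete only when drop-out depends on observed data. For example, take a true difference of 1.4, SD 2.1 per period change, and let the 4 patients with the largest observed period-1 rise on glimepiride leave. The t-test then averages 1.11 to 1.26 for rho 0 to 0.5, and the mixed model 1.40. A patient lost before the first week-12 test has no change score and adds nothing to either.

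**7. The data-collection rules side by side.**

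| Patient | 5.3 | 5.8.1 | 5.9 |
|---|---|---|---|
| Withdraws consent | – | collection ends | collection ends |
| Non-compliant, still consents | continues | collection ends | no ban stated |
| Stops drug for an adverse event | continues | no ban stated | no ban stated |

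For LF:HF the conflict is confined to the second row. Under the assumption in step 5, each drop-out whose HRV is kept in both periods lowers the shift by 1.4/45 = 0.031.

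**The case against.** **The plan already has an analysis of all the data.** A reader might infer that nothing planned can use one-period patients. That goes too far. The longitudinal model in 12.2, read naturally, keeps them and yields a week-12 treatment effect. It is only a partial answer: it is labelled exploratory, and Table 1 schedules HRV only at the baseline and end visit of each period, so there are no LF:HF values at weeks 4 and 8. The 12-week mixed model could keep them too. But it is introduced as the counterpart of the t-test and may be taken to inherit the both-period set.

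**Section 5.8.1 is narrower than it looks.** A reader might infer that data collection ends for anyone who stops study drug. It does not: adverse-event stops are outside its ban. Section 5.9 also lets the investigator withdraw a subject for behavioral reasons, so removal for non-compliance is not in itself contrary to 5.9. What remains is that 5.3 promises research activities for all randomized participants, while 5.8.1 forbids them for a group that has not withdrawn consent.

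**The forms do not settle it.** The Completion Data form lists non-compliance as a reason for leaving, from which a reader might infer that practice follows 5.8.1. But the Medication Compliance form lists non-compliance as a reason for stopping study drug and then asks whether it was restarted, which fits continued participation.

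**The size is assumed and small.** This stands. Nothing in the documents supports a 1.4 gap. The larger ratio of 0.47 SE needs SD 2.1 for the paired difference, which does not reproduce the 38 patients. The 4 or 5 losses cover all causes, and no count is given for non-compliance. The protocol also calls the study a pilot.

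**Conclusion.** The point holds on the text. With no imputation rule, the ITT t-test excludes every one-period patient from the comparison of the drugs. Read per endpoint, it duplicates the primary comparison. It is therefore no check on drop-out, although 10% non-completion is planned for and losses are not replaced. Sections 5.3, 5.8.1 and 5.9 also give conflicting instructions on collecting the primary endpoint from non-compliant patients who still consent.

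The documents do not support a claim of material bias. The precision at stake is 0.5 to 2.3 equivalent pairs, for rho between 0.8 and 0. The shift of 0.12 to 0.16 (0.27 to 0.33 SE) rests wholly on an assumed 1.4 gap. On that same assumption the mixed model would recover at most half of it. The case for change is that the defect is certain, the remedy is already in the protocol, and HRV not collected cannot be recovered later.

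**What to change.** **1. Analysis.** In 12.1.1 and 12.2, replace the ITT repeat of the t-test with the planned 12-week mixed model (treatment, period, sequence, random subject) on all treated patients with at least one period's LF:HF change. Report it beside the both-period analysis, which can stay primary. State its limits:
- it relies on data being missing at random;
- recovery is only partial if drop-outs' drug effect itself differs;
- patients lost before the first week-12 test add nothing.

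**2. Data collection.** For protocol non-compliance only, reconcile 5.8.1 with 5.3 and 5.9, so that patients who have not withdrawn consent keep the scheduled end-of-period HRV visits. No position is taken on when study drug is stopped or restarted.

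**3. Separate note.** Section 5.8.1 ends data collection on pregnancy, while 13.2 requires the pregnancy outcome to be followed. These must be reconciled on their own terms. This does not bear on LF:HF, and no position is taken on clinical management or research visits there.

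**Cost.** Protocol and SAP wording, plus a few visits already on the schedule that would otherwise be skipped. The downside is that some off-treatment data enter the mixed-model estimate. The report should say so.

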12.1.2 Safety analysis set

All patients will be evaluable for toxicity from the time of their first treatment. All safety laboratory measurements (see section 6.4.5) and any reported or observed AEs (see section 6.4.3) will be documented in source document.

12.2 Methods of statistical analyses

The primary objective of this trial is to compare the change in the LF: HF ratio from baseline to 12 weeks for patients on dapagliflozin versus glimepiride.

The mean change in LF: HF ratio for each drug from baseline to 12 weeks will be reported with the corresponding 95% confidence interval. The mean difference between drugs of changes from baseline to 12 weeks and the corresponding 95% confidence interval will also be reported. The change from baseline to 12 weeks within each period (between drugs) will be compared within patients using a two-sided t-test (applying transformations where appropriate; using the pharmacodynamics set of subjects). This analysis will be repeated using the ITT set of subjects. If there is chance within-subject or between-subject imbalance in baseline measures (such as glucose control, BMI and age), we will use the ANCOVA method including those unbalanced covariates to improve precision (Metcalf, *Statistics in Medicine, The analysis of cross-over trials with baseline measurements*, 2010).

A corresponding primary analysis to the t-test controlling for possible sequence and period effects includes a linear mixed effects model (also known as random effects model; applying transformations where appropriate) with outcome of the change in LF: HF ratio from baseline to 12 weeks. This model assesses the difference between drugs by accounting for a

random effect for subject (nested within sequence) and fixed effects for treatment, sequence, and period.

We will additionally explore differences between the drugs over time using all of the data measured at baseline, 4, 8 and 12 weeks with a linear mixed model. The outcome will be the change from baseline at 4, 8 and 12 weeks. The model will include a random term for subject nested within sequence and fixed effects for treatment, sequence, visit, period, and interaction terms for visit by treatment. The interaction terms for visit by treatment provide estimates of treatment effects at each visit. An unstructured variance/covariance matrix will be used.

All secondary endpoints will be similarly compared where each endpoint for each drug will be measured at baseline and 12 weeks and the difference within each drug will be compared within patients using a two-sided t-test (applying transformations where appropriate). Similar to the analysis for the main outcome, linear mixed effect models with an unstructured variance/covariance matrix and outcomes of changes from baseline at 4, 8, and 12 weeks will assess changes over time for each outcome. The mixed effects models will include a random effect for patients nested within sequence and fixed effects for treatment, sequence, visit, period and the interaction between treatment and visit.

Associations between the indices of glucose variability and changes in measures of HRV during each intervention will be analyzed using paired t-tests or Wilcoxon signed rank test (if normality assumption is violated). Effect sizes will be estimated with 95% confidence intervals of the associations between glucose variability and changes in measures of HRV within each intervention using linear regression (applying transformations when necessary). If period effects are found from our primary analysis, we will control for the period in which the drug was given within the model. The interaction between drug and glucose variability on the changes in measures of HRV will be explored using a generalized estimating equations (using an unstructured working correlation matrix since we only have 2 observations per person). We will not control for multiple comparisons and expect results to be validated in a future independent cohort.

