3. STUDY PLAN AND PROCEDURES

3.1 Overall study design and flow chart

This is a 26-week, single-center, randomized, single-blinded to the investigators, open-label, 2-period crossover phase IV clinical trial comparing 12-weeks of glycemic intervention with dapagliflozin versus glimepiride on measures of HRV. The two periods will be separated by a 2-week wash-out period. All subjects will be allocated and randomized to each treatment sequence in a 1:1 fashion. Participants will receive either dapagliflozin 5 mg or glimepiride 2 mg daily initially for 4 weeks then titrating the dose gradually up to dapagliflozin 10 mg daily or glimepiride 4 mg daily (no more than 4 mg daily) as needed based on glucose monitoring for 8 more weeks (total 12 weeks) followed by 2-week washout period. Then they will receive the study drugs in reverse order to the first period for another 12 weeks. Glucose variability will be also assessed using Abbott's Freestyle Libre Pro CGM for 2-week during each intervention period.

Figure 1: Proposed study design

[figure not shown]

Table 1: Proposed visit schedule

	Period 1					Wash-out	Period 2			
Visit Numbers	Visit 1	Visit 2	Visit 3	Visit 4	Visit 5		Visit 6	Visit 7	Visit 8	Visit 9
Visit Description	Screening	Baseline Visit (Study Drug 1)	Monitoring	Monitoring	End of Study Drug 1	N/A	Baseline Visit (Study Drug 2)	Monitoring	Monitoring	End of Study Drug 2
Time point	Day -30 to 0	Day 0	Week 4	Week 8	Week 12	Week 13-14	Week 15	Week 19	Week 23	Week 26
Visit window	1 month	± 7 days	± 7 days	± 7 days	± 7 days	NA	± 7 days	± 7 days	± 7 days	± 7 days
Informed consent and HIPPA ¹	X									
Medical history	X				X		X			X
Physical exam ²	X				X					X
Inclusion/Exclusion criteria	X									
Concomitant medications	X						X			
Vital signs	X	X	X	X	X		X	X	X	X
Urine analysis, urine β-HCG test in women of childbearing age	X									
Venous blood A1C	X				X					X
CBCP, FBG, comprehensive metabolic profile, , lipid profile, and urine albumin excretion	X				X					X
TSH	X									
BNP	X				X		X			X

ECG	X				X		X			X
HRV		X			X		X			X
CARTs		X			X		X			X
CGM				2 weeks					2 weeks	
Assess hypoglycemia		X	X	X	X		X	X	X	X
Record Adverse Events (AEs), Serious Adverse Events (SAEs)		X	X	X	X			X	X	X
Assessment of compliance by counting pills			X	X	X			X	X	X

¹ The informed consent form must be signed before any study procedure is performed.

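### The primary mixed model cannot represent a negative correlation between the two period changes, so its standard error may be too small if the subject variance is bounded at zero

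*Combined protocol and SAP*

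**What the plan says.** Section 12.2 analyses the change in LF:HF from baseline to week 12 within each period. It first gives a within-patient two-sided t-test. It then gives a mixed model, also called primary, that adjusts for sequence and period through a "random effect for subject (nested within sequence) and fixed effects for treatment, sequence, and period". For this model it states no residual covariance, no rule on whether the subject variance may go negative, and no degrees-of-freedom method. An unstructured covariance is specified only for the longitudinal models at weeks 4, 8 and 12. Section 12.2 does not say which primary analysis governs.

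Section 12.1.1 restricts the primary set to patients with endpoint data in both periods. A secondary analysis uses an ITT set of everyone who took at least one dose.

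Section 12.3 bases the sample size on the t-test, "using a two-sided (paired) t-test at the 0.05 significance level", and states: "We assume there are no carryover effect and no interactions between patients, treatments, and time period". Section 3.1 has patients "randomized to each treatment sequence in a 1:1 fashion". Its Table 1 places HRV testing at Visits 2, 5, 6 and 9 (day 0 and weeks 12, 15 and 26, each ±7 days), with a 2-week washout between periods.

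**The concern.** A random subject intercept suits outcomes that share a stable patient level. Here that level has already been removed, because each change subtracts its own period's baseline. What remains can be uncorrelated between periods, or negatively correlated: Visit 5 ends the first change and Visit 6 starts the second, the two visits are only 2-3 weeks apart, and their values enter with opposite signs.

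A random-intercept variance is a covariance between the two changes. If the software holds it at zero or above, a negative covariance cannot be fitted. The estimate goes to zero and the two mean squares are pooled, which understates the variance of the treatment contrast. The result is a confidence interval that is too narrow and a false-positive rate above 5% in the one primary analysis that adjusts for period.

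**Working it through.** **Inputs from section 12.3.** Two-sided alpha 0.05; "80% power with 38 patients"; "differences in LF: HF ratios of 1.4"; "within person standard deviation (2.1) of the difference of the differences"; and "Expecting 10% of the subjects to not complete the entire study, we plan to enroll 45 patients".

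**Reproducing the plan's figure.** The crossover formula is n = 2 × [SD(z₁ + z₂)/difference]² = 2 × [2.1 × (1.960 + 0.842)/1.4]² = 2 × 17.66 = 35.3, so 36. With the t distribution and an SD of the between-drug difference of 2.1√2 = 2.97, n = 38 with power 80.7%. So 38 reproduces when 2.1 is the per-period within-patient SD. Read literally, as the SD of the difference of differences, 2.1 gives 18 (normal) or 20 (t). For 10% dropout, 38/0.9 = 42.2, so 43; the plan enrols 45. This sets n but says nothing about the between-period correlation ρ.

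**What ρ could be.** The documents give no value, so each line below rests on the assumption stated in it.
- *Additive patient effect, independent errors* (consistent with section 12.3): the patient effect cancels in each change and ρ = 0.
- *AR(1), weeks 0, 12, 14, 26, 2-week correlation r:* ρ = (2r⁷ − r − r¹³)/[2(1 − r⁶)] = −r(1 − r⁶)/2. At r = 0.2 this is −0.10, at 0.7 it is −0.31 and at 0.9 it is −0.21.
- *AR(1), weeks 0, 12, 15, 26 as in Table 1:* about −0.05 to −0.26 over the same r, and −0.02 to −0.12 if half the variance is measurement error.
- *Serial decay with 12-week correlation 0.3-0.7 and measurement error 0-20% of variance* (either gap, with or without a stable patient component): −0.02 to −0.31.
- *A patient response common to both drugs,* with variance τ² relative to the change-score error variance: ρ = τ²/(1 + τ²), which is +0.09 at τ² = 0.1 and +0.33 at τ² = 0.5.

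**Effect on the standard error.** For balanced complete pairs, the treatment contrast has SE = √(2s²/n). The correct s² is the within-patient mean square, with expectation σ²(1 − ρ), where σ² is the variance of one period's change. The between-patient mean square has expectation σ²(1 + ρ). REML with the subject variance held at ≥ 0 uses the within-patient mean square when it is the smaller of the two, and otherwise the average of both, with expectation σ². When truncation is nearly certain, the SE is therefore about 1/√(1 − ρ) of its true value: 1/√1.2 = 0.91 at ρ = −0.2 and 1/√1.3 = 0.88 at ρ = −0.3. Direct numerical REML matched this closed form to about 3 parts in a million.

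**Type I error,** n = 38, one million simulated trials per row:

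| ρ | Variance truncated at 0 | Mean SE / true SE | Type I, df n−2 | Type I, Satterthwaite-type df |
|---|---|---|---|---|
| +0.3 | 3% | 0.99 | 5.0% | 5.0% |
| +0.2 | 11% | 0.99 | 5.1% | 5.1% |
| +0.1 | 28% | 0.98 | 5.2% | 5.3% |
| 0 | 50% | 0.96 | 5.6% | 5.8% |
| −0.1 | 72% | 0.94 | 6.2% | 6.5% |
| −0.2 | 89% | 0.91 | 7.0% | 7.4% |
| −0.3 | 97% | 0.87 | 8.1% | 8.6% |

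The within-patient contrast, or the same model with an unbounded variance or unstructured covariance, stayed at about 5.0% in every row, with mean SE 0.99 of the true value. Results at n = 40 were nearly the same.

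**The case against.** Several points on the other side are sound.

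- The negative correlation is assumed. Section 12.3 supports ρ = 0, not a negative value, and at zero the excess is only 0.6-0.8 percentage points. Values of 7% or more need ρ near −0.2 or below.
- Subtracting baseline removes a patient's level but not a response shared by both periods. Sections 1.3 and 3.2 aim at similar glucose lowering with both drugs, so a shared response is plausible. It would make ρ positive and remove the problem, although section 12.3 assumes patient interactions away.
- The zero bound is a software convention that the plan does not state. The listed terms are those of the classical 2x2 crossover ANOVA. On complete pairs, testing treatment against the within-patient mean square is exact at every ρ, and the text permits that.
- The 0.05 level in section 12.3 is attached to the paired t-test, which is listed first and is unaffected. The study also calls itself a pilot (sections 6.9 and 12.4).

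These points make the problem conditional and limit its size, but they do not remove it. The text permits an exact test without securing one. The mixed model is also the only primary analysis that estimates a period effect, and section 12.2 makes the period adjustment of the glucose-variability regressions depend on whether the primary analysis finds one. For the GEE on two values per patient, section 12.2 already chooses a fully free correlation. The primary model lacks that freedom.

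**Conclusion.** The point holds conditionally. If ρ is zero or negative and the subject variance is bounded at zero, the primary mixed model understates its standard error. Under section 12.3's own assumptions the excess is under one percentage point. Under the serial-correlation models above, type I error ranges from little more than the ρ = 0 figure up to about 8.6%. If ρ is +0.2 or more there is no material inflation.

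A reader might infer that the trial's false-positive rate necessarily exceeds 5%, or that it may reach 10% or more. The documents do not support either. They give neither ρ nor a variance bound, one of the two primary analyses is immune, and rates above 10% arise only near ρ = −0.5 (10.4-11.0%), which is outside every range derived here.

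**What to change.** In section 12.2, replace the random intercept in the primary mixed model with an unstructured 2x2 within-patient covariance by period, or explicitly allow an unbounded subject variance. State a small-sample degrees-of-freedom method, such as Kenward-Roger. On complete pairs this is equivalent to comparing within-patient period differences between the two sequences, with n − 2 degrees of freedom. Also say whether this model or the paired t-test governs.

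The cost is a sentence or two of text and a slightly wider interval. Data collection and sample size do not change. Fitting subject as a fixed effect would also protect the type I error, but it absorbs the sequence term, and ITT patients with only one period would then add nothing to the treatment contrast. The unstructured covariance is therefore preferable for the ITT analysis.
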